2. OBJECTIVES

Primary objective:

To study whether FoodforCare at Home is superior to usual care with respect to quality of life in advanced abdominal cancer patients undergoing chemotherapy.

Secondary objectives:

1. To reduce diet-related symptoms in these patients by using FoodforCare at Home compared to usual care.
2. To improve nutritional intake (adequate protein and energy intake) in these patients by using FoodforCare at Home compared to usual care.
3. To improve the nutritional status of these patients by using FoodforCare at Home compared to usual care.
4. To improve the functional status of these patients by using FoodforCare at Home compared to usual care.
5. To reduce medication use for the purpose of treating diet-related symptoms in these patients by using FoodforCare at Home compared to usual care.
6. To improve quality of life of the partners/caregivers of these patients by using FoodforCare at Home compared to usual care.
7. To improve patient satisfaction towards nutrition in these patients by using FoodforCare at Home compared to usual care.

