6. METHODS

6.1 Study parameters/endpoints

6.1.1 Main study parameter/endpoint

Quality of life:

The main study parameter is the quality of life of advanced cancer patients using FoodforCare at Home. Quality of life will be evaluated using the EORTC-QoL-C30 at every time point. This is a validated questionnaire for measuring quality of life in palliative patients [38]. The global quality of life and the functional scales will be included as the main items in determining the quality of life of the patients. The symptom scales will be analyzed as secondary endpoint. Questionnaires will be scored according to the procedures specified by the EORTC [39].

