Medication use will be evaluated at every time point by obtaining information from the medical file of the patients. Information will be cross-checked by the researcher on doses and frequency of medication use. During the intervention period, medication use will be assessed by asking patients to log on a diary when they used which medication including dosage.

Symptoms:

To assess the number and the severity of symptoms experienced by the patients, they are asked to fill in the 'Utrecht Symptoom Dagboek' every day for 3 weeks during the intervention period. This is a diary based on the ESAS which consists of 12 symptoms which are frequently experienced by palliative cancer patients [46]. On a scale from 0 to 10, patients can score the severity of the symptoms with 0 indicating no symptom and 10 indicating the worst possible symptom.

Patient satisfaction:

The Net Promoter Score (NPS) with additional questions will be used to assess patient satisfaction in the intervention group at time point 3. The NPS is determined by asking the question: 'How likely is it that you would recommend FoodforCare to a friend or colleague?'. The score ranges from 1-10 and patients can be grouped in 'promoters' (9-10 grading), 'passively satisfied' (7-8 grading) and 'criticasters' (0-6 grading). The NPS is finally calculated by subtracting the percentage of criticasters from the percentage of promoters [47]. Additional questions about satisfaction with respect to the food supply and logistics of FoodforCare at Home will be answered by the patients to explain their score. The control group will also receive a questionnaire about their wellbeing and way of shopping and cooking. Both questionnaires are self-composed and based on validated questionnaires because there is no Dutch validated questionnaire available about a home-delivered meal service.

During the pilot study, participants in the intervention group are asked to participate in an in-depth interview instead of the questionnaire. This interview will be led by one of the researchers. It will generate information about the home-delivered meal service so it can be improved when implemented in the RCT.

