8.3 Secondary study parameter(s)

The courses over time and the difference between the groups will also be analyzed for the secondary outcomes. The continuous variables like quality of life of the caregiver, nutritional status (hand grip strength, PG-SGA), nutritional intake and performance scale will be analyzed the same way as the primary outcome. The course over time and the difference between the groups in medication use like anti-emetics e.g. will be treated as a dichotomous outcome (yes/no) and analyzed by using the Chi-square test. The difference in patient satisfaction and severity of symptoms between the two groups will be analyzed using the independent samples t-test.

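### Symptom severity is tested with an unadjusted t-test, although daily diary scores, pre-intervention symptom scores and a mixed model are already in the plan

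*Combined protocol and SAP*

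**What the plan says.** Section 2 lists as its first secondary objective: "To reduce diet-related symptoms in these patients by using FoodforCare at Home compared to usual care".

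Two instruments measure symptoms:

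- **Diary (Section 6.1.2).** Patients complete it "every day for 3 weeks during the intervention period". It covers 12 symptoms, each scored 0 to 10. Section 3 places it in the intervention period only, so there is no pre-intervention diary score.
- **QLQ-C30 (Section 6.1.1).** "The symptom scales will be analyzed as secondary endpoint". Section 3 and Table 1 schedule the questionnaire at all four time points. T1 precedes chemotherapy and is named as the baseline. T2 is at the second cycle, when the intervention begins.

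On analysis, Section 8.3 opens: "The courses over time and the difference between the groups will also be analyzed for the secondary outcomes". It then names caregiver quality of life and nutritional status as examples of continuous outcomes and adds that "nutritional intake and performance scale will be analyzed the same way as the primary outcome", meaning the mixed model of Section 8.2. Symptoms are not among the examples. For them the section says: "The difference in patient satisfaction and severity of symptoms between the two groups will be analyzed using the independent samples t-test".

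Section 8.3 does not say which diary symptoms are tested, how the 21 days are summarised, or what happens to incomplete diaries. Section 8.1 states intention-to-treat without a missing-data rule. Section 6.6 covers only withdrawal after T3.

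**The concern.** A t-test compares one number per patient between two groups. Three things are lost when it is applied to a three-week daily diary.

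1. It cannot show how the groups diverge over the cycle, which the opening sentence of Section 8.3 says will be examined.
2. It makes no use of symptom levels before the intervention, although Section 4.4 relies on baseline adjustment for the primary outcome.
3. It gives a patient who stops the diary in week 1 the same weight as one who completes it, or leaves that patient out. These are palliative patients on chemotherapy, with 20% drop-out planned. If those who feel worse stop sooner, the days on record are not representative of the three weeks.

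At stake are the precision and the possible bias of the symptom result. The primary analysis is not affected.

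**Working it through.** **The plan's own adjustment factor.** Section 4.4 uses a difference of 10, SD 22, two-sided alpha 0.05 and 80% power:

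n per arm = 2 × (1.960 + 0.842)² × 22² / 10² = 76, as stated.

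It then multiplies its drop-out-inflated total of 180 by 1 − ρ² with ρ = 0.3: 180 × 0.91 = 163.8, or 164, as stated. (How 152 becomes 180 is a separate matter and does not affect this factor.)

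**Precision lost by omitting a baseline.** The variance factor is 1 − ρ², and the equivalent gain in patients is 1/(1 − ρ²) − 1.

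| ρ | Source | Variance factor | Variance cut | Equivalent extra patients |
|---|---|---|---|---|
| 0.3 | Section 4.4, primary outcome | 0.91 | 9% | 10% |
| 0.5 | assumption | 0.75 | 25% | 33% |
| 0.6 | assumption | 0.64 | 36% | 56% |

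For scale, borrow the primary outcome's standardised difference, 10/22 = 0.4545, and take 164 × 0.8 / 2 = 65.6 evaluable patients per arm:

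- Unadjusted: Φ(0.4545 × √(65.6/2) − 1.96) = Φ(0.643) = 74.0% power.
- Adjusted at ρ = 0.3: Φ(2.603/√0.91 − 1.96) = Φ(0.769) = 77.9% power.

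The gain is about 4 points. The documents state no power for symptoms.

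**What averaging the diary keeps.** With intraclass correlation ICC (assumed), the variance of a 21-day mean relative to one day is ICC + (1 − ICC)/21. This is 0.52 at ICC 0.5 and 0.71 at ICC 0.7. A t-test on complete 21-day means therefore keeps most of the repeated-measures information. A t-test on a single day does not, and the plan does not say which is meant.

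**Early diary stops.** The documents give no stop rates, so this is illustration only. The simulation used 66 patients per arm and 1,000 runs per scenario. All of the following are assumptions:

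- The mean score starts at 3.5 and rises 0.05 per day.
- Between-patient SD is 1.6, slope SD 0.06 and day-to-day SD 1.2.
- The true effect is either nil or grows linearly to 1.0 point, averaging −0.50 over the three weeks.
- The chance of stopping rises with the previous day's score. It is either the same function in both arms or higher with usual care.

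| True mean difference | Stopping rule | Stopped early, meals / usual care | Mixed model | Mean of available days | Completers only |
|---|---|---|---|---|---|
| 0 | same | 33% / 33% | 0.00 | 0.00 | 0.00 |
| 0 | higher with usual care | 33% / 51% | 0.00 | +0.05 | +0.31 |
| −0.50 | same | 28% / 33% | −0.50 | −0.41 | −0.42 |
| −0.50 | higher with usual care | 28% / 51% | −0.51 | −0.37 | −0.11 |

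In the last row the available-day mean falls short by 0.50 − 0.37 = 0.13, or 26% of the effect. The estimate varied between simulated trials with an SD of about 0.30, so the shift is 0.13/0.30 = 0.43 of a standard error. The mixed model was given the true covariance, which favours it. Estimating the variance components instead did not change the picture when checked.

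**The case against.** The strongest reply is that the sentence in Section 8.3 is ordinary shorthand for comparing one summary per patient. On that reading the test is valid, and for an unpowered secondary outcome the choice between a per-patient mean and a mixed model is largely one of efficiency. At ρ = 0.3 the gain is small. The simulated stopping depends on observed scores, a mechanism under which a mixed model does well. Even there, the available-day mean is off by only 0.05 on a 0 to 10 scale when there is no effect. The large errors belong to a completers-only test, which the plan does not propose.

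Most of this stands, and it limits the size of the point. It does not remove the conflict within Section 8.3 over the course over time, nor the absence of any baseline or rule for incomplete diaries.

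Three stronger readings are tempting but are not supported:

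- **That the 21 daily records will be pooled as if independent**, with a grossly inflated type I error. No section says so. The text speaks only of a difference between two groups.
- **That the QLQ-C30 symptom scales also get only a t-test.** Section 6.1.2 uses severity in describing the diary, and the list of outcomes sent to the mixed model is given as examples. The scales may already be covered there.
- **That symptoms rank above the other secondary outcomes.** The objectives are numbered, but no hierarchy is stated.

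**Conclusion.** The concern holds as a worthwhile improvement to a secondary analysis. The stated t-test is valid on per-patient summaries with complete diaries. It still cannot deliver the course over time that its own section promises, and it forgoes baseline information already collected.

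The precision loss is 9% of variance at the documents' only correlation, which was stated for the quality-of-life outcome and is borrowed here. It would be 25 to 36% only if the correlation between the T1 symptom score and the diary were 0.5 to 0.6. Because the diary has no pre-intervention score, that correlation is between two different instruments and is unknown.

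Bias from early stopping is possible, but its size and direction depend on stop rates that the documents do not give. The simulated figures show what could happen and are not a forecast.

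**What to change.** In Section 8.3, replace the t-test for diary symptoms with a linear mixed model on the daily scores:

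- Include a patient random effect, group, day, group-by-day and the stratification factors (tumour type and type of chemotherapy).
- Adjust for a related QLQ-C30 symptom score at T1 where one exists. Use T2 only if it is completed before allocation is known. Section 3 randomises before the second cycle and Section 6.3 leaves patients unblinded, so that order is not assured.
- Report the group difference in mean score over the three weeks, and name in advance which of the 12 symptoms count as diet-related.

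State separately that the QLQ-C30 symptom scales are analysed with the primary outcome's mixed model.

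With T1 as the covariate, no new data or procedures are needed. The cost is SAP wording and slightly more analysis. The model relies on missing at random: given the recorded scores and covariates, stopping must not depend on the unrecorded ones. The SAP should say so.

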8.4 Interim analysis

No interim analyses will be performed in this study.

9. ETHICAL CONSIDERATIONS

9.1 Regulation statement

This study will be directed according to the principles of the World Medical Association Declaration of Helsinki (64th WMA General Assembly, October 2013). Additionally, is it in agreement with the Medical Research Involving Human Subjects Act (WMO) and other guidelines, regulations and Acts.

9.2 Recruitment and consent

Patients will be recruited through the department of Medical Oncology at the Radboud University Medical Centre in Nijmegen. All patients admitted to this department en those who meet the inclusion criteria are asked to participate in the study. This request will be discussed with the patient by the nurse or one of the researchers. Additionally, patients will receive a patient information letter with further information about the study. When everything is clear and the patient is willing to participate in the study, the informed consent will be signed. When a patient is enrolled in the study, a personal number is assigned by one of the researchers. The researcher documents the patients' data and the personal number in a designated protected document.

9.3 Objection by minors or incapacitated subjects

Not applicable.

9.4 Compensation for injury

There is a standard liability insurance available at the Radboud University Medical Centre for the study subjects. This is also written in the patient information letter. For the investigators there is also a liability insurance arranged at the Radboud University Medical Centre. In the proposal letter accompanying this protocol, we asked for release of a liability insurance for study subjects because this study includes usual nutritional care and meal service from FoodforCare which is already implemented in the medical centre. The patients will not be exposed to medical treatments during this study.

9.5 Incentives

Patients will not receive financial compensation for participating in the study. They will not have to pay additional hospital visits for this study and thus, they will have no additional travel costs or other costs. However, the intervention group will receive the meals and food products from FoodforCare for free. Due to the measurements that will be performed 3 months after the intervention period, it will not be possible to continue with the FoodforCare meals after this period. Once the effectiveness of FoodforCare at Home has been demonstrated, it is likely that the meals will become available for regular use.

10. ADMINISTRATIVE ASPECTS, MONITORING AND PUBLICATION

10.1 Handling and storage of data and documents

All study documents will be stored in the investigator site file. The informed consent forms will also be stored in Epic. The researchers will enter all data into the database of Castor by means of the study number with their personal password. Only the researchers who are directly involved in the study have access to this program. The key to the codes will be stored in a secure digital environment, so the privacy and anonymity of the patients is ensured. Both the written data and the entered data in Castor will be stored for up to 15 years after the study.

10.2 Monitoring and Quality Assurance

Looking at the directives of the NFU for on-site monitoring, the monitoring-class of the study is negligible. Minimum monitoring is indicated. The monitoring will be performed by an independent gastroenterologist according to the monitoring plan.

Monitorplan

Monitor Frequency	Once halfway the inclusion
Patient flow	Inclusion rate and drop-out percentage
Trial Master File/ Investigator File	Presence and completeness of research file
Informed Consent	100%
In-/exclusie Criteria	First 3 subjects, thereafter 10%
Source Data Verification	10%

10.3 Amendments

Not applicable with first version of the research protocol.

10.4 Annual progress report

The investigator will submit a summary of the progress of the trial to the accredited METC in case the study takes longer than a year. In this report, information will be provided on the date of inclusion of the first subject, numbers of subjects included and numbers of subjects that have completed the trial, serious adverse events/ serious adverse reactions, other problems, and amendments.

10.5 End of study report

The investigator will notify the accredited METC of the end of the study within a period of 8 weeks. The end of the study is defined as the last patient's last visit. For this study, this will be after the last measurement moment of the last patient.

In case the study is ended prematurely, the investigator will notify the accredited METC within 15 days, including the reasons for the premature termination.

Within one year after the end of the study, the investigator/sponsor will submit a final

study report with the results of the study, including any publications/abstracts of the study, to the accredited METC.

10.6 Public disclosure and publication policy

After analyzing all data, the goal is to present the results on (inter)national conferences and to publish the results in an international journal, independently on positive or negative results of the study. This will be agreed with the sponsor in a contract.

11. STRUCTURED RISK ANALYSIS

11.1 Potential issues of concern

A risk analysis, in respect to the cooperation contract between Maison van den Boer and the Radboud University Nijmegen Medical Centre, will be described in the Aanbiedingnotitie to the Board of Directors and will also be contracted. For example, the risk of financial loss will be clearly described in this contract. This letter will also disclose that FoodforCare has no influence on publishing (positive or negative) results.

11.2 Synthesis

As described previously, we expect that this meal concept will have no additional risk to the patients. In daily practice, the dishes of FoodforCare are widely offered to all patients in the hospital. Matters such as patient safety and hygiene will be respected. In light of these arguments, it does not seem necessary to us to give a structured risk analysis.

